4.3 Secondary Objective(s)

N/A

4.4 Secondary Estimand

N/A

5 STUDY DESIGN

5.1 Description of Study Design

This is a phase 3, multicenter, uncontrolled, open label, nonrandomized study conducted at approximately 20 sites in the US. Approximately 185 subjects will be enrolled. All eligible subjects will have mild to moderate DED (inclusion criteria number 4).

5.1.1 Description of Study Duration

The study is expected to be completed in approximately 7 months. The expected study duration for each subject is 37 days with 30 ± 5 days of IP exposure.

The study will consist of a Screening visit, Baseline visit on Day 1, Remote Compliance Check on Day 14, and an Exit visit on Day 30.

Refer to Section 2.2 for more information and [Figure 2-1](#) for an outline of the study.

Selected population according to the inclusion/exclusion criteria is representative of the target population for the product.

6.2 Inclusion Criteria

Written informed consent must be obtained before any study specific assessment is performed. Upon signing the informed consent, the subject is considered enrolled in the study.

Subjects eligible for inclusion in this study must fulfill **all** of the following criteria:

1. Subject must be at least 18 years of age at the time of informed consent.
2. Subject must be willing and able to understand and sign an IRB/IEC approved informed consent form.
3. Subject must be willing and able to attend all required study visits and complete subjective questionnaires.
4. Subject must exhibit symptoms of dry eye at the Screening visit (IDEEL- SB ≥ 16 and ≤ 65).
5. Subject must have BCVA equal to or better than 20/80 (or ≥ 55 letters score or ≥ 0.6 ETDRS logMAR) in each eye at the Screening visit.
6. Subject must have NITBUT of > 5 and < 10 seconds in each eye at the Screening visit.
7. Subject must meet at least one of the 3 conditions below at the Screening visit (based on the criteria below):
 - a. ADDE as indicated by a TMH of < 0.2 mm
 - b. EDE as indicated by a meibum quality score of ≥ 1 (on a 0 to 3 scale) or meibum expressibility score of > 1 (on a 0 to 3 scale) in either eye lid (lipid deficient (or evaporative) dry eye subgroup) measured by the Meibomian Gland Functionality Test.
 - c. MDE as indicated by meeting both entry criteria (a) and (b) above (mixed dry eye subgroup).
8. Subject must be willing to discontinue use of all artificial tear supplements and use only the study product as directed starting at Visit 2/Day 1.
9. Subject must be willing and able to connect to and use electronic patient reported outcomes with their mobile device to [REDACTED] record daily IP usage information.

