2.3 Schedule of Study Procedures and Assessments

Table 2-2 provides a summary of the schedule of study procedures and assessments.

Table 2-2 Schedule of Study Procedures and Assessments

Visit	Visit 1 Screening	Visit 2 Baseline	Visit 3 Remote Compliance Check	Visit 4 Exit	Unscheduled Visit	Early Exit
Study Day and Visit Window	2 to 7 days prior to Visit 2	Day 1	Day 14 ± 3 days	Day 30 ± 5 days		
Informed consent	X					
Connect to electronic patient reported outcomes	X ⁹	X		X	(X)	X
Demographics	X					
Medical history	X					
Concomitant medications	X					
Changes to concomitant medications or medical history		X	X	X	X	X
Urine pregnancy test ¹	X			X	(X)	X
Inclusion/exclusion	X					
Meibomian gland functionality test ¹	X					
BCVA (OD, OS; logMAR; distance)	X	X		X	(X)	X
IDEEL-SB Questionnaire ⁸	X			X		X

Visit	Visit 1 Screening	Visit 2 Baseline	Visit 3 Remote Compliance Check	Visit 4 Exit	Unscheduled Visit	Early Exit
Study Day and Visit Window	2 to 7 days prior to Visit 2	Day 1	Day 14 ± 3 days	Day 30 ± 5 days		
Slit lamp biomicroscopy examination (with corneal staining)	X	X		X	X ⁷	X
Administer IP (IP instillation on site)		X				
Adverse events	X	X	X	X	X	X
Device deficiencies	X	X	X	X	X	X
Distribute subject instructions		X			(X)	
Dispense IP		X			(X)	
Collect used and unused IP				X	(X)	X
Remote compliance check			X			

(X) Assessments performed as necessary

¹ Source Only

⁷ Assessment performed as necessary for unplanned dispense visit

⁸ Electronic patient reported outcomes unless otherwise specified by sponsor

⁹ Screening may be rescheduled within 7 days/1 week if connection cannot be established. All remaining criteria will be verified after completing connection.

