9.3.4 Best Corrected Visual Acuity

LogMAR visual acuity using the ETDRS and/or SOC chart for both eyes must be performed.

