11 PROTOCOL DEVIATIONS

Per ICH E6 (GCP) R2 Section 4.5.1 the investigator/institution should conduct the study in compliance with the protocol agreed with the sponsor and, if required, by the regulatory authority and which was given approval/favorable opinion by IRB/IEC.

Protocol waivers or deviations from the protocol inclusion and exclusion criteria are not allowed because they can potentially jeopardize the scientific integrity of the study regulatory acceptability or Subject safety. Therefore, adherence to the criteria as specified in the protocol is essential.

The site will contact the sponsor for clarification of inclusion and/or exclusion criteria as needed prior to enrollment of the study subject. The sponsor or their representative will document clarification requests and responses. If a Subject does not meet any of the eligibility criteria, that Subject may not be enrolled into the study.

If the investigator feels that in his/her clinical judgment, it is necessary to promptly implement reasonable alternatives to, or deviations from, the protocol in consideration of the safety of study subjects, the sponsor is to be notified of these alternatives and deviations, and the reasons for such changes are to be documented in the study records. The investigator is to also notify his/her IRB/IEC of any such changes.

If a significant protocol deviation is identified by the investigator or through site monitoring activities, an immediate submission to the IRB/IEC may be required (as per IRB/IEC guidelines). The sponsor will assess any protocol deviation and decide whether any of these non compliance should be reported to the relevant competent authority as a serious breach of Good Clinical Practice (GCP) and the protocol. If per the relevant competent authorities' requirements, the protocol deviation is not required to be reported immediately but is still required to be notified to the IRB/IEC, the specific protocol deviation will be added to the annual progress report.

The sponsor will review, designate, and/or approve all protocol deviations prior to the database lock.

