**Table 1–1 Study Description Summary**

Study Design	Phase 3, multicenter, single-arm, open label, nonrandomized
Study Population	Mild to moderate dry eye disease (DED) subjects $\geq 18$ years of age with an IDEEL-SB score $\geq 16$ and $\leq 65$ , best corrected visual acuity (BCVA) equal to or better than 20/80 in each eye, noninvasive tear break-up time (NITBUT) $> 5$ and $< 10$ seconds in each eye [REDACTED] [REDACTED] [REDACTED] will be included in this study.  Target to complete: 143 Planned to enroll: ~185
Number of Sites	~ 20 United States
Investigational Product	FID123300
Planned Duration of Exposure	~ 30 days  At Visit 2/Day 1, subjects will receive one drop of investigational product (IP) per eye in the morning.  On Days 2 to 30 $\pm 5$ (including day of) subjects will self-administer at least one drop per eye 4 times daily.  On Visit 4/Day 30 $\pm 5$ , subjects will self-administer the last drop per eye 30 minutes prior to visit.
Visits	Visit 1 – Screening Visit 2 – Baseline/Day 1 (occurs 2-7 days after Visit 1) Visit 3 – Remote Compliance Check (Day 14 $\pm 3$ days)

	Visit 4 – Day 30/Exit (Day 30 ± 5 days)
--	---

A study design schematic is depicted in [Figure 1–1](#).

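### Inclusion criterion 5 states the logMAR acuity limit with its inequality reversed (≥ 0.6), contradicting the 20/80 and 55-letter limits in the same sentence

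*Protocol*

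**What the plan says.** Protocol section 6.2, criterion 5, sets the acuity limit at Screening: "BCVA equal to or better than 20/80 (or ≥ 55 letters score or ≥ 0.6 ETDRS logMAR) in each eye". The main clause is in Snellen notation, and the parenthesis restates it as a letter score and as a logMAR value.

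SAP Table 1-1 describes the population by the Snellen version alone: "best corrected visual acuity (BCVA) equal to or better than 20/80 in each eye".

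Three other places bear on how the criterion is read:

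- Protocol Table 1-2 expands logMAR as the log of the minimum angle of resolution.
- Protocol Table 2-2 lists BCVA for each eye in logMAR, and section 9.3.4 states: "LogMAR visual acuity using the ETDRS and/or SOC chart for both eyes must be performed". SAP section 5.3.2 also summarises BCVA in logMAR.
- Protocol section 11 states: "Protocol waivers or deviations from the protocol inclusion and exclusion criteria are not allowed". Section 6.5 does not let a screen failure be rescreened.

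**The concern.** A larger minimum angle of resolution means worse vision, so logMAR runs opposite to acuity and to letter score. A floor on letters should therefore become a ceiling on logMAR. Criterion 5 puts a floor on both.

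The contradiction sits in a binding eligibility rule at about 20 sites, and the faulty expression is in the unit that the schedule names for BCVA. Whether a given eye complies depends on which of the three expressions is checked. A screener or an edit check that compares the recorded logMAR value with the protocol's logMAR limit would admit eyes at 20/80 or worse and reject better ones. A subject wrongly rejected could not be rescreened. A subject wrongly admitted would fall outside the population in SAP Table 1-1, yet could be said to meet one expression of the criterion.

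**Working it through.** **Inputs**

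- Snellen limit: 20/80 or better (protocol section 6.2, criterion 5; SAP Table 1-1).
- Letter limit: "≥ 55 letters score" (criterion 5).
- LogMAR limit: "≥ 0.6 ETDRS logMAR" (criterion 5).
- Direction of the logMAR scale: from the definition in protocol Table 1-2.
- Letter conversion: letters = 85 − 50 × logMAR, that is, 0.02 logMAR per letter with 85 letters at logMAR 0. This is the usual ETDRS convention and is an assumption here, because the documents give no conversion.

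**Step 1: reproduce the cut-point.** LogMAR = log10(Snellen denominator / 20).

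- 20/80: log10(80/20) = log10(4) = 0.602, nominally 0.6.
- 55 letters: (85 − 55) × 0.02 = 0.60.

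The three numbers describe the same acuity, so the figure of 0.6 is correct.

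**Step 2: apply each inequality.** LogMAR is rounded to one decimal, and letters are computed from the rounded value.

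| Snellen | logMAR | Letters | 20/80 or better | ≥ 55 letters | logMAR ≥ 0.6 (as written) | logMAR ≤ 0.6 |
|---|---|---|---|---|---|---|
| 20/20 | 0.0 | 85 | pass | pass | **fail** | pass |
| 20/40 | 0.3 | 70 | pass | pass | **fail** | pass |
| 20/63 | 0.5 | 60 | pass | pass | **fail** | pass |
| 20/80 | 0.6 | 55 | pass | pass | pass | pass |
| 20/100 | 0.7 | 50 | fail | fail | **pass** | fail |
| 20/125 | 0.8 | 45 | fail | fail | **pass** | fail |
| 20/160 | 0.9 | 40 | fail | fail | **pass** | fail |
| 20/200 | 1.0 | 35 | fail | fail | **pass** | fail |

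The logMAR limit as written agrees with the other two only at the cut-point. With the sign turned round, all three agree on every row.

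**Step 3: count over the letter scale.** For whole scores 0 to 100 (101 values) under the assumed conversion:

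- ≥ 55 letters accepts 55 to 100: 100 − 55 + 1 = 46 scores.
- LogMAR ≥ 0.6 accepts 0 to 55: 55 + 1 = 56 scores.
- Both accept only the score 55, which is 1 score.
- Either accepts 46 + 56 − 1 = 101 scores, which is all of them.
- They disagree on 101 − 1 = 100 scores.
- LogMAR ≤ 0.6 accepts the same 46 scores as the letter limit.

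**Step 4: what each literal reading does.** Taken as alternatives joined by 'or', the criterion excludes no eye. Taken as three joint requirements, it admits only eyes at the cut-point. Taken by the logMAR figure alone, it inverts the intended population.

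**The case against.** The strongest reply is that no competent site would be misled. The Snellen limit is the operative clause, the letter score agrees with it, and the logMAR figure is the second of two parenthetical restatements. Anyone who applied logMAR ≥ 0.6 would reject 20/20 eyes and would see the conflict with the opening words of the sentence. SAP Table 1-1 gives the Snellen rule cleanly. Section 11 tells sites to ask the sponsor for clarification of eligibility criteria before enrolment, and the manual of procedures, which is not available here, may state the limit correctly. The primary endpoint is a questionnaire score, and BCVA is a descriptive safety variable. Finally, the counts over the letter scale only restate that a sign is reversed; they do not say how many subjects are affected.

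Much of this stands. The intent is clear, the natural reading is the Snellen one, and the documents give no acuity distribution from which to estimate affected subjects. The counts measure how far the expressions conflict, not the expected number of errors. But none of these points corrects the criterion. The clarification route helps only a site that notices the problem, and no visible passage restates the logMAR limit the right way round. The error also remains in the unit used to record BCVA, under a section 11 rule that permits no departure from the criteria.

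**Conclusion.** The point holds. The logMAR inequality in criterion 5 is reversed. The proof needs only the stated Snellen limit, the protocol's own expansion of logMAR and log10(80/20) = 0.602. The letter-score comparison corroborates it and rests on the assumed conversion.

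The error should be fixed, although it does not threaten the primary analysis: hypotheses, test and alpha are untouched. What it puts at risk is consistent screening, deviation classification and monitoring. The documents do not show which expression sites actually apply, so whether any subject has been affected cannot be determined from them.

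**What to change.** Reconcile the three expressions in criterion 5 with each other and with SAP Table 1-1. LogMAR ≤ 0.6 is the form that agrees with the Snellen and letter limits already stated, so no new threshold is involved. Because 20/80 is 0.602 before rounding, the text should say that 0.6 is the nominal (rounded) value, so that an eye at exactly 20/80 is not failed on the third decimal. Check that any edit check or eligibility worksheet built from criterion 5 uses the same direction.

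The cost is one character and a short note on rounding, by amendment or clarification letter. If screening has begun, add one listing of Visit 1 BCVA for enrolled subjects and of screen failures attributed to criterion 5, each compared with 20/80 or better in each eye.

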6.3 Exclusion Criteria

Subjects meeting any of the following criteria will be excluded and may not participate in this study. Criteria are assessed at Screening/Visit 1.

1. History of hypersensitivity to the study drug or any of its excipients or to drugs of similar chemical classes.
2. Women who are pregnant or breastfeeding at the time of study entry or who plan to become pregnant during the study.
3. Ocular abnormalities that could adversely affect the safety or efficacy outcome such as:
 - a. Eyelid anomalies that affect proper lid closure or proper blink function (e.g., ectropion or entropion).
 - b. Corneal disorders or abnormality such as active corneal ulcer, current corneal abrasion, keratoconus, or corneal dystrophies which are actively changing or affect vision.
 - c. Metaplasia of the ocular surface.
 - d. History of corneal erosion syndrome or recurrent corneal erosion syndrome.
 - e. Clinically significant corneal epithelial anterior membrane dystrophy (patients with minor/insignificant primary peripheral corneal epithelial dystrophy (not central dystrophy) without a history of corneal erosion syndrome can be included).
 - f. Current filamentous keratitis.
 - g. Evidence of corneal neovascularization.
 - h. Any history of herpes simplex or herpes zoster keratitis.
4. Uncontrolled active systemic diseases. These conditions may include but are not limited to conditions that in the opinion of the investigator would preclude study participation, including unstable diabetes, thyroid diseases, autoimmune diseases, and/or poorly controlled hypertension.

5. Active ocular infection (bacterial, viral, or fungal) or active inflammation not associated with dry eye such as uveitis, iritis, active blepharitis, active ocular allergies or active allergic conjunctivitis, etc.
6. Current or past participation in any clinical study within 30 days prior to the Screening visit.
7. Punctal plug insertion or diathermy procedure initiated within 30 days prior to the Screening visit.
8. Lid hygiene therapy initiated ≤ 4 weeks prior to the Screening visit. Note: Patients who have been on a consistent lid hygiene therapy (i.e., no change to the type of lid hygiene therapy being used or to the frequency of use) for more than 4 weeks prior to the Screening visit are not excluded. However, they cannot stop or change this regimen for the duration of the study. In addition, patients who do not currently use lid hygiene therapy cannot start the regimen while participating in the study.
9. Individuals who were treated with thermal pulsation treatments or other lid treatments in either eye in the last 12 months. Patients cannot be treated with thermal pulsation treatments or other lid treatments while participating in the study.
10. Any significant illnesses that could, in the opinion of the investigator, interfere with the study parameters.
11. Use of any systemic medication known to cause dry eye (e.g., antihistamines, antidepressants, antipsychotics, benzodiazepines, etc.) for less than 1 month before the Screening visit. If patient is on a stable regimen for at least a month prior to the Screening visit, the dosing regimen must not change for the duration of their participation in this study. In addition, patients who do not currently use any of these medications cannot start a regimen while participating in the study.
12. Contact lens use within one month prior to Screening visit and unwilling to avoid contact lens use during the course of the study.
13. History of ocular or intraocular surgery, eyelid surgery, keratorefractive procedure, corneal transplant, or serious ocular trauma, within 6 months prior to the Screening visit.
14. Initiation of any new topical ocular medication (over the counter or prescribed) ≤ 60 days prior to the Screening visit. Note: Patients on Restasis®, Cequa® (cyclosporine ophthalmic emulsion), or lifitegrast ophthalmic solution 5% (Xiidra®), must be on therapy for at least 6 months prior to the Screening visit.

6.4 Lifestyle Considerations

6.4.1 Other Activity

Subjects will be advised to maintain and be in a consistent environment and refrain from swimming on Day 1.

6.5 Screen Failures and Rescreening of Subjects

A screen failure occurs when a subject who consents to participate in the clinical study does not meet inclusion/exclusion criteria. A minimal set of screen failure information is required to ensure transparent reporting of screen failure subjects to meet the Consolidated Standards of Reporting Trials (CONSORT) publishing requirements and to respond to queries from regulatory authorities. Minimal information includes demography, screen failure details, eligibility criteria, and any serious adverse events (SAEs).

Individuals who do not meet the criteria for participation in this study (screen failures) may not be rescreened.

Subjects will not be replaced.

After signing the informed consent form (ICF), subjects will be asked to establish a connection to the electronic patient reported outcomes (ePRO) (inclusion criteria number 9) prior to any other assessments. In the event this connection cannot be established, subjects will be allowed to reschedule the Screening visit within 7 days/1 week. All remaining criteria will be verified after completing inclusion criteria number 9. In case the subject is not willing to reschedule or the Screening visit can't be rescheduled within the specified window, the subject will be considered a screen failure.

Enrollment number may be increased based on the tracking of number of completers.

6.6 Study Eye Selection Criteria

Study subjects will be dosed in both eyes.

7 INVESTIGATIONAL PRODUCT AND CONCOMITANT THERAPY

7.1 Description of Investigational Product

This study will investigate the IP in a single period. The expected duration of subject participation is approximately 37 days; IP exposure is approximately 30 ± 5 days. Visit 1/Screening will occur 2 to 7 days prior to Visit 2/Day 1 Baseline. At Visit 2/Day 1 Baseline,

subjects will administer one drop of IP per eye. [REDACTED]

[REDACTED] Starting on Day 2, subjects will administer at least one drop of IP per eye 4 times daily through to Visit 4/Exit. The Visit 3/Remote Compliance Check will occur on Day 14 ± 3 days [REDACTED] Visit 4/Exit will occur on Day 30 ± 5 days. On Visit 4/Exit, subjects will administer at least one drop of IP per eye 4 times with their last drop 30 minutes prior to the visit.

More information on the IP can be found in the IB.

7.2 Rationale for Investigational Product

This study design is justified based upon an evaluation of the results of relevant preclinical and clinical testing, as described within the IB.

7.3 Dosing and Administration

This study is evaluating the effect of 1) one ophthalmic drop of IP in each eye on Day 1 and 2) at least one ophthalmic drop of IP in each eye 4 times daily (additional usage as needed) after 30 ± 5 days on subjects with DED.

There are no time requirements within each day (e.g., morning, afternoon, night) for daily dosing from Day 2 to Day 30 ± 5. On Visit 4/Exit, subjects should administer one drop of IP in each eye 4 times with the last ophthalmic drop administered approximately 30 minutes prior the visit. Subjects should follow drop administration requirements. Instructions for delayed or missed drop administration will be outlined within the MOP/instructions.

Table 7-1 Dosing Regimen

Intervention:	FID123300
Dosing Regimen:	At Visit 2/Day 1, subjects will receive one drop of IP per eye in the morning. [REDACTED] [REDACTED] [REDACTED] [REDACTED] On Days 2 to 30 ± 5 (including day of) subjects will self-administer at least

	one drop per eye 4 times daily. On Visit 4/Day 30 ± 5, subjects will self-administer at least one drop per eye 4 times with the last drop per eye approximately 30 minutes prior to Visit 4.
--	---

7.4 Treatment of Overdose

The components of this product are considered pharmacologically inert, non-toxic, and nonirritating. Therefore, no toxic effects are to be expected. For more information refer to IB.

7.5 Preparation, Handling, Storage, and Accountability

7.5.1 Preparation of Investigational Product

No special preparation is needed. Subjects will be dispensed two bottles at Day 1. If subjects require resupply, subjects should contact the site.

For more information refer to the IFU.

7.5.2 Handling and Storage of Investigational Product

Compound Number:	FID123300
Manufacturer	Alcon Laboratories, Inc. [name]
Indication for use and intended purpose in the current study	For the temporary relief of burning and irritation due to dryness of the eye
Product description and parameters available for this study	Propylene Glycol 0.6% Lubricant Eye Drops

Formulation	Refer to IB for details.
Number/Amount of product to be provided to the subject	Subject will receive two 11 mL bottles of IP with a 10 mL fill. Subjects will return to office for spare IP.

Labeling description	Label shall include the information below, at minimum: 
 • FID number • Lot number/batch number • Expiration date • Content statement • Investigational statement • Sponsor information • Temperature/storage conditions
Training and/or experience requirements for device	No additional training or experience is required to administer the IP.
Storage conditions	15 – 25°C (59 – 77°F) Refer to MOP for details regarding temperature monitoring.
Additional information	N/A
Supply	The IP will be provided by the study sponsor prior to the start of the study. Refer to the MOP for a detailed description.

